5.7 Pivotal definitions

5.7.1 Time zero

To define many outcomes, e.g., **S2**: “new episode of neutropenic fever within 28 days”, we need to precisely define when the time starts. This is necessary to properly define the time window, e.g. “within 28 days”. In this SAP, we define that time (i.e., time zero) at the time of treatment initiation, not at time of randomization, which should occur appropriately 48 hours later. This is consistent with the definition of the primary outcome (see Section 4.1) and it should facilitate the interpretation of the results.

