4.1 Primary objective, endpoint and estimand

The two treatment strategies (interventions) being investigated are the following.

- **Experimental (“short”):** discontinuation of antibiotics, despite neutrophil count $< 0.5 \times 10^9$ cells/L, after 48 hours of apyrexia and clinical stability. A child is considered clinically stable by the treating physician when there is resolution of all symptoms and signs of infection, and normalization of vital signs including heart rate, respiratory rate, oxygen saturation, blood pressure, and daily diuresis.
- **Control (“standard” or “long”):** discontinuation of antibiotics when either i) neutrophil count is $\geq 0.5 \times 10^9$ cells/L, and the child is afebrile and clinical stable or ii) the child has received 10 days of antibiotics and has been afebrile and clinically stable for 7 days.

The two treatment strategies are followed from randomization until neutrophil recovery (i.e. neutrophil count $\geq 0.5 \times 10^9$) or 28 days, whichever comes last. In case of relapsing fever, the patients continue to be treated according to the same treatment strategy (“short” or “long”). Randomization could occur from 36 hours after initiation of antibiotics until 48 hours of apyrexia and clinical stability (when the two treatment strategies can start to differ).

The primary outcome is the number of days without antibiotic treatment within the first 28 days after treatment initiation. For each of the 28 days, the information of whether the patient received antibiotics has been collected. The typical reasons for restarting antibiotics are new onset of fever, typically:

- febrile neutropenia (without documented infection)
- fever with or without neutropenia due to a possible or proven bacterial infection, including bacteremia (bacterial infection in the blood stream), pneumonia, skin infection, gastroenteritis or typhilitis (infection in the gut), urinary infection or other types of focal infections; side effects to chemotherapy that is accompanied by fever, such as pancreatitis

Restarting antibiotics might also happen without new onset of fever, for instance in case of suspicion of infection (e.g. focal symptoms from skin, lungs, gastrointestinal, etc).

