The primary clinical question of interest is: *“Is the mean number of days alive without antibiotic treatment, within 28 days after treatment started, larger when children receive the “short” treatment duration strategy than when they receive the “long”, among children with cancer who started antibiotic treatment for high risk neutropenic fever of unknown origin, regardless of any intervention”*

during the follow-up needed to ensure good clinical care?

Accordingly, the primary estimand is described by the following attributes:

- Population: children (aged 0-17) with cancer receiving antibiotic treatment for high risk neutropenic fever of unknown origin 48 hours after presentation. In particular, children with
 - a single temperature of at least 38.5° C , or a temperature above 38.0° C sustained over a 1-hour period (auricular, oral or rectal), at presentation.
 - an absolute neutrophil count $< 0.5 \times 10^9$ cells/L and an expected duration of neutropenia of more than 7 days at presentation.
 - a negative blood culture (or other clinically relevant culture) 48h after the start of the culture.
- Endpoint: number of days alive without antibiotic treatment within the first 28 days after treatment initiation.
- Treatment: The investigational interventions (“short” vs “long”, as defined above) regardless of adherence and of any subsequent treatment decision or intervention during the follow-up needed to ensure good clinical care (“treatment policy strategy”, see [14]).
- The intercurrent event “any subsequent treatment decision or intervention needed to ensure good clinical care” is addressed by the treatment condition of interest attribute (“treatment policy strategy”, see [14]). The intercurrent event adherence to the investigational intervention is also addressed by the treatment condition of interest attribute (“treatment policy strategy”, see [14]). There are no other relevant intercurrent events anticipated.
- Population-level summary: Difference in means between treatment conditions.

Remarks:

- (i) The “treatment policy strategy” for the intercurrent event “adherence to the investigational intervention” is consistent with an Intention-To-Treat principle/analysis discussed in Section 5.1. In our context, “adherence” is defined as “continue antibiotic treatment” as long as defined by the treatment strategy (not shorter, not longer).

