5.7.2 Duration of treatment

Treatment durations are computed as the time difference between two dates and times: that of treatment stop and that of treatment start. Hence, treatment durations expressed in days are not whole numbers, but decimal numbers. Time of start and stop are defined as the first and last times when the treatment was administered to the patient. This definition of treatment duration is used to define the primary outcome and in the computation of some rates (See Section 10.1.1).

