5.7.4 Neutropenia and episode of neutropenic fever

To define **S2** (New episode of neutropenic fever within 28 days), we also need to define neutropenia. Start of neutropenia is defined as the time when neutrophil counts are first observed $< 0.5 \times 10^9$. Time of stop of neutropenia is defined as the first time neutrophil count is observed $\geq 0.5 \times 10^9$ after start time. An episode of neutropenic fever starts when the child is first observed with both neutropenia and fever. It stops when either fever or neutropenia stops (whichever comes first).

Durations of neutropenia expressed in days are computed as the time difference between two dates and times: that of neutropenia stop and that of neutropenia start. Hence, treatment durations expressed in days are not whole numbers, but decimal numbers. This definition of neutropenia is used to compute secondary outcome **S2** and some rates (See Sections 4.2).

6 Analysis Sets

- The “**All episodes analysis set**” consists of all randomized episodes.
- The “**Per protocol analysis set**” consists of all randomized episodes except those for which the child did not receive the “short” or “long” treatment strategy to which he or she was randomized. These children will be identified as detailed in Section 10.2.3.

7 Analyses supporting the primary objective

The main analysis supporting the primary objective and corresponding to the estimand detailed in Section 4.1 will use the “All episodes analysis set” and corresponds to an ITT analysis.

To estimate the between arm difference in means with a 95% confidence interval and a p-value, we will use a multiple linear model (aka ANCOVA). The model will be fitted via GEE [17] and the standard errors will be computed accordingly, to account for possible within-patient correlation, as already mentioned in Section 5.5. We will use an independent working correlation structure, as we expect the correlation to be negligible and because additional assumptions might be needed for other choices [24]. The variance and link functions that define the GEE will be that of a gaussian family with an identity link, as commonly used for quantitative outcomes. Baseline covariates included in the model will be:

²pricisely, that of fever stop or 28 days after treatment initiation, whichever comes first (because we compute the sum within 28 days).

- Age at randomization

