10.2.2 Baseline characteristics

Baseline characteristics will be descriptively summarized per arm, using the “All episodes analysis set”. The list of baseline variables to be summarized includes:

- Sex (male/female)
- Age (year)
- Study site
- Year of inclusion (Nov 2020 to Dec 2021, 2022, 2023 or 2024)
- Cancer disease and treatment cycle (ALL induction, ALL not induction, AML, Relapsing ALL, Lymphoma, Neuroblastoma, Other)
- Days from cancer diagnosis to randomization
- Empirical antibiotic treatment at randomization
- ANC at presentation
- Minimum ANC within the time interval ranging from presentation to randomization
- Thrombocyte count at presentation
- Neutropenia duration at randomization

For quantitative variables, we will present median, first and third quartiles and also minimum and maximum. Categorical variables will be summarized by counts and percentages. The number and proportions of missing values, if any, will be reported for each variable, per arm. Hypothesis tests will not be performed to compare baseline characteristics, but clinical importance of any imbalance will be noted. This is in line with usual recommendations [21].

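### Antibiotic time before randomization counts in the primary outcome and can vary more than the SAP's 48-hour description suggests, yet it is neither adjusted for nor listed at baseline; the cost is precision, not bias

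*SAP*

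**What the plan says.** Three statements in the SAP bear on when a child enters.

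- Section 5.7.1 puts time zero "at the time of treatment initiation, not at time of randomization, which should occur appropriately 48 hours later".
- The population attribute in Section 4.1 describes "children (aged 0-17) with cancer receiving antibiotic treatment for high risk neutropenic fever of unknown origin 48 hours after presentation".
- The description of the strategies in Section 4.1 says: "Randomization could occur from 36 hours after initiation of antibiotics until 48 hours of apyrexia and clinical stability". It adds that this closing point is when the two strategies can begin to differ.

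The outcome is the "number of days alive without antibiotic treatment within the first 28 days after treatment initiation". Section 5.7.2 measures treatment time on a continuous scale: "Time of start and stop are defined as the first and last times when the treatment was administered to the patient".

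The Section 7 model adjusts for age (from "Age at randomization"), cancer type, ANC and thrombocyte count at presentation, and site. The code in A.1 matches that list of variables. Section 10.2.2 lists two durations that end at randomization, days from cancer diagnosis and "Neutropenia duration at randomization", but not time from antibiotic start to randomization. Section 5.6 gives a gain in power as one reason for adjusting.

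**The concern.** The window closes at a point set by fever resolution, not by hours since antibiotic start. A child last febrile on day 6 may be randomized as late as day 6 + 2 = day 8. The 48-hour description therefore fits only some of the children whom the window admits.

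Because the outcome clock starts at antibiotic start, the time before randomization uses up part of the 28-day window in either arm. It is fixed before allocation and so is a legitimate baseline covariate. If it varies materially and predicts the outcome, leaving it out adds avoidable residual variance in a trial whose stated power at 100 episodes is 64%. As it is not among the listed baseline items, the planned table would not show its spread or balance directly.

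**Working it through.** **Inputs from the SAP.** Difference 3 days (16 versus 13), SD 6.5, two-sided 5%, 1:1 allocation (Sections 5.2 and 11.1); about 100 episodes expected (Section 11.2).

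**Inputs assumed.** The SD of time from antibiotic start to randomization, s, is not given; 1, 2 and 3 days are used. The slope b of the outcome on that time, averaged over arms, is not given either.

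**1. The plan's own figures.** n per arm = 2 × 6.5² × (1.96 + 1.282)² / 3² = 98.7, rounded up to 99; total 198; 198/0.9 = 220. At n=100, SE = 6.5 × √(4/100) = 1.30 and power = Φ(3/1.30 − 1.96) = 63.6%, against the stated 64%. These reproduce.

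**2. What slope do the stopping rules in Section 4.1 imply?** Ignore relapses and take the last fever on day 1, 3 or 6.
- Short arm: the stop falls 48 hours later, on day 3, 5 or 8. Each extra febrile day removes one antibiotic-free day. For children randomized near the close of the window the slope on entry time is near -1.
- Control arm, second rule (10 days of antibiotics and 7 days afebrile and stable): the stop falls on day 10, 10 or 13. Between day 1 and day 3 the slope is 0.
- Control arm, first rule: neutrophil recovery can set the stop, which weakens the link further.

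The average slope is therefore short of -1. Simulating these rules under assumed fever courses gave about -0.2 to -0.6 in the control arm, against about -1 in the short arm when entry is late. A range of -0.5 to -0.75 is used as the working average.

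**3. Power after adjustment at n=100.** R² = b²s²/6.5², with 6.5² = 42.25; SE = 1.30 × √(1 − R²); power = Φ(3/SE − 1.96).

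| s (days) | b = -0.5: R², SE, power | b = -0.75: R², SE, power |
|---|---|---|
| 1 | 0.006, 1.296, 63.9% | 0.013, 1.291, 64.2% |
| 2 | 0.024, 1.285, 64.6% | 0.053, 1.265, 66.0% |
| 3 | 0.053, 1.265, 66.0% | 0.120, 1.220, 69.1% |

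For comparison, b = -1 in both arms gives 64.6%, 67.9% and 73.9%. That is a ceiling the control-arm rules do not support. Direct simulation of the rules gave about 64-68% in most scenarios, 71% at the extreme, and 63.6% (no gain) when entry clusters near 48 hours.

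**4. Validity without adjustment.** In 3,000 simulated trials per scenario, with 50 independent episodes per arm, the unadjusted estimate averaged about 0 under the null and 3.0 under the alternative. Type I error was 4.2-4.5%.

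**5. Cost of an uninformative covariate.** The Section 7 model has 1 intercept + 1 treatment + 3 age + 3 cancer + 2 ANC + 3 thrombocyte + 2 site = 15 coefficients. One more inflates the variance by about 1 + 1/84 at n=100, where 84 = 100 − 16. SE becomes 1.308 and power 63.1%, a loss of about half a point.

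**The case against.** The strongest reply has four parts.

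*The gain may be nil.* In the short arm the stop depends on fever duration, not on when the child was randomized, so entry time is only a proxy. If most children were randomized near 48 hours, as Section 5.7.1 expects, the slope is about 0. This stands, and it is why the size is given as a range starting at no gain.

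*Covariate choice is a reasoned judgement.* Section 5.6 commits to a few covariates, and Section 12 says the list was reconsidered without any preliminary outcome analysis. That stands too; the point is a cheap improvement, not an error in the test. Time to randomization nevertheless fits the SAP's own aim of gaining power, because it is built into the outcome's clock.

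*The 48-hour wording is an expectation and enters no calculation.* That is true of Section 5.7.1. The population phrase may also refer to the 48-hour culture result. No estimate changes with either phrase, but the population is an estimand attribute and should agree with the entry window.

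*Imbalance would not be wholly hidden.* The list in Section 10.2.2 is worded as open, and the plot in Section 10.2.7 shows antibiotic days for each patient. That stands; what is lacking is a direct summary by arm.

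A reader might infer that each day before randomization removes a full antibiotic-free day in both arms, so that a chance imbalance carries over day for day. The control-arm stopping rules do not support that. A reader might also infer a biased comparison. The variable precedes allocation and is balanced in expectation, and the standard error already covers chance imbalance.

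**Conclusion.** The concern holds as one of precision and description. The window in Section 4.1 permits entry well after 48 hours, the outcome clock includes that time, and the plan neither adjusts for it nor lists it at baseline. The likely benefit of adjustment is small to moderate: from about 0 to 5 power points around a base of 63.6% at n=100 (69.1 − 63.6 = 5.5 at the top of the table). It rests on two quantities that the SAP does not give, the SD of entry time and the average slope. It also ignores any overlap with the existing covariates, which would reduce it. The primary test remains valid as written, and the sample size figures are not in question.

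**What to change.** 1. Before outcome data are examined, add time from antibiotic start to randomization, continuous and linear, to the Section 7 covariates and to the model in A.1. If outcome data have already been examined, run it as a labelled sensitivity analysis instead.
2. Add the same variable to Section 10.2.2, summarized by arm.
3. Reconcile Section 5.7.1 and the population attribute in Section 4.1 with the randomization window in Section 4.1. Time zero can stay as it is.

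The cost is some wording and a sixteenth coefficient, worth about half a power point if the variable proves uninformative. No new data should be needed: antibiotic start times are recorded, and the baseline durations already planned require the randomization date.

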5.7.2 Duration of treatment

Treatment durations are computed as the time difference between two dates and times: that of treatment stop and that of treatment start. Hence, treatment durations expressed in days are not whole numbers, but decimal numbers. Time of start and stop are defined as the first and last times when the treatment was administered to the patient. This definition of treatment duration is used to define the primary outcome and in the computation of some rates (See Section 10.1.1).

5.7.3 Fever and episode of fever

Fever is pivotal to define **S2** and **S3**. We say that a child has fever when the child fulfills (at least) one of these two conditions: a) a single temperature $\geq 38.5^\circ \text{C}$ once or b) temperature $\geq 38.0^\circ \text{C}$ sustained within one hour. An episode of fever starts as soon as we observed condition

a) or b). That is, as soon as a single temperature ≥ 38.5 is observed or once we have observed a temperature ≥ 38.0 for one hour (whichever comes first). An episode of fever stops 48 hours after the last time we observe the child with fever. That is, 48 hours after the last time a temperature ≥ 38.5 is observed or 48 hours after the last we have observed a temperature ≥ 38.0 for one hour, whichever comes last. Accordingly, a new episode of fever cannot start before 48 hours after the last time we observed condition a) or b). The temperature was monitored very regularly (≥ 1 per day) as is standard in this population of children with cancer.

To define **S3** (Days alive without fever within 28 days), we sum the duration of all episodes of fever within 28 days. A fever duration is computed as the time difference between two dates and times: that of fever stop² and that of treatment start. Hence, fever durations expressed in days are not whole numbers, but decimal numbers.

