4.2 Secondary endpoints

There are five secondary outcomes:

S1: Severe adverse event (SAE) within 28 days, defined as any of these events:

- Severe sepsis, defined as either (i) vasoactive treatment requirement or (ii) fluid bolus requirement $>20\text{mL/kg}$ or (iii) respiratory support requirement (mechanical ventilation).

- Fever with positive blood culture. For possible contaminants, at least two positive culture bottles were required. Possible contaminants include coagulase negative staphylococcus, micrococcus spp., non hemolytic streptococcus, Corynebacterium spp, Propionibacterium spp, Bacillus spp.
- Severe focal infection highly suspicious of bacterial cause, requiring antibiotic treatment (e.g. lungs, abdomen, CNS, skin)
- Death

S2: New episode of neutropenic fever within 28 days.

S3: Days alive without fever within 28 days.

S4: Mortality within 28 days.

S5: Time to bone marrow recovery (up to 3 month), defined as the time from start of treatment to first absolute neutrophil count (ANC) $\geq 0.5 \times 10^9$ cells/L.

Note: see Section 5.7 for details about the definitions of fever, neutropenia/neutropenic, **S2** and **S3**.

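### The S3 rule measures every fever episode from treatment start, so any relapse is counted back to day 0 and days without fever come out too low, sometimes negative

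*SAP*

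**What the plan says.** Section 4.2 lists the outcome as "S3: Days alive without fever within 28 days", a quantity that can only lie between 0 and 28. Section 5.7.1 sets time zero at treatment initiation.

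Section 5.7.3 then gives the derivation:

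- Onset of a fever episode is defined: "An episode of fever starts as soon as we observed condition" a) or b), the two temperature criteria.
- Its end is defined: "An episode of fever stops 48 hours after the last time we observe the child with fever".
- Several episodes per child are foreseen: "a new episode of fever cannot start before 48 hours after the last time we observed condition a) or b").
- For S3, "we sum the duration of all episodes of fever within 28 days".
- The length of each is fixed as follows: "A fever duration is computed as the time difference between two dates and times: that of fever stop" "and that of treatment start. Hence, fever durations expressed in days are not whole numbers, but decimal numbers".

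Footnote 2 to that section refines the first of the two times: "that of fever stop or 28 days after treatment initiation, whichever comes first". It leaves the second as treatment start.

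**The concern.** The onset of a fever episode is defined and then not used. As worded, a fever episode's duration is simply its stop time on the trial clock, and S3 subtracts the sum of those stop times. That is harmless for a child with one episode present at treatment start and wrong for every child whose fever returns.

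Relapse is not a remote case in this trial. Section 4.1 provides for relapsing fever and names new fever as the typical reason for restarting antibiotics, S2 is a new episode of neutropenic fever, and Section 10.1.2 analyses rates of new fever episodes.

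Because the error falls only on children with recurrent fever, it is differential whenever recurrence differs between arms. If fever recurs more often after early stopping, S3 is biased against the short strategy. The error would also enter the descriptive summaries of S3 in Section 10.2.5 and the subgroup repeat of S3 in Section 10.1.4.

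**Working it through.** The SAP states no expected value for S3, so there is no figure to reproduce. The check applies the rule to example fever histories. These are assumptions, not trial data. Times are days from treatment start, each stop time is the end of the fever episode as Section 5.7.3 defines it, and the child survives 28 days.

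**Formulas**

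- As written: S3 = 28 − Σ min(stop, 28)
- Measured from each episode's own onset: S3 = 28 − Σ [min(stop, 28) − max(onset, 0)]

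The two differ by Σ max(onset, 0). So S3 as written is too low by the sum of the onset days of all fever episodes that begin after treatment start.

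| Fever episodes (days) | Fever days as written | S3 as written | Actual fever days | Correct S3 | Shortfall |
|---|---|---|---|---|---|
| 0–4 | 4 | 24 | 4 | 24 | 0 |
| 0–4, 14–17 | 4 + 17 = 21 | 7 | 4 + 3 = 7 | 21 | 14 |
| 0–4, 21–25 | 4 + 25 = 29 | −1 | 4 + 4 = 8 | 20 | 21 |
| 0–4, 26–30 (capped at 28) | 4 + 28 = 32 | −4 | 4 + 2 = 6 | 22 | 26 |
| 0–4, 14–17, 22–26 | 4 + 17 + 26 = 47 | −19 | 4 + 3 + 4 = 11 | 17 | 14 + 22 = 36 |

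S3 is negative whenever the capped stop times add to more than 28. It is always negative when a first episode is followed by one that reaches day 28, because the first stop plus 28 exceeds 28. The footnote's cap does not prevent this.

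**Does other text correct the origin?** No. Appendix A.4 takes the days variable as already derived. The sibling definitions use the start of the same state: treatment stop minus treatment start in Section 5.7.2, neutropenia stop minus neutropenia start in Section 5.7.4. Only the fever rule departs from that pattern.

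**Effect on the mean difference (short minus long).** The shift is roughly the between-arm difference in later fever episodes per randomised episode, times their mean onset day. With an assumed 0.2 more in the short arm and onset at day 15: 0.2 × 15 = 3 spurious days.

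**Effect on the median difference (short minus long),** which is the S3 estimand (Sections 4.3 and 8.2). A median moves far only when nearly half of an arm has corrupted values. Simulations with assumed relapse rates, fever lengths and relapse times gave these ranges across settings:

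| Relapse, long vs short | Correct median difference | As written |
|---|---|---|
| 30% vs 30% | about 0 | about 0 |
| 10% vs 20% | −0.3 to −0.4 | −0.3 to −0.5 |
| 20% vs 30% | −0.4 | −0.4 to −0.8 |
| 30% vs 40% | −0.4 to −0.6 | −0.7 to −1.5 |
| 30% vs 50% | −0.8 to −1.2 | −4.2 to −5.4 |

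In one such simulation the mean difference went from −0.4 to −1.9 at 20% vs 30% (a shift of 1.5 = 0.1 × 15) and from −0.8 to −4.0 at 30% vs 50% (3.2 = 0.2 × 16), in line with the approximation above. The share of negative S3 values at 30% vs 50% ranged from 0% to 18%, depending on the assumed fever lengths and timing.

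**The case against.** The best reply is that this is a drafting slip, not a chosen method. The sentence follows the template of Section 5.7.2, and the same residue appears in Section 5.7.4, where the neutropenia paragraph closes by speaking of treatment durations. The endpoint's name, the definition of fever onset and the instruction to sum episode durations all point to fever start as the intended origin. Literal use might also reveal itself, since negative counts would show up in the minimum reported under Section 10.2.5.

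The reach is limited too. S3 is one of five secondary outcomes and is reported without a hypothesis test (Section 5.3). The primary outcome uses Section 5.7.2, and S2 depends on whether a new episode starts, not on how long it lasts. The estimand is a difference in medians, which hardly moves at low relapse rates, and a bias against the short strategy presupposes more relapse in that arm.

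All of this is fair, and it limits the size of the problem. It does not remove it. The sentence is the only operational definition of S3. A programmer who follows it gets wrong values, many of them plausible (7 instead of 21), so a range check would not catch them all. One who silently corrects it departs from the signed plan in an open-label trial.

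**Conclusion.** The concern holds. As written, the rule is correct only for fever already present at treatment start; for every fever episode that begins later, it understates S3 by that episode's onset day and can produce impossible negative values. That follows from the text alone.

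The size of the effect on the arm comparison rests on relapse rates that the SAP does not give. The median difference is almost unaffected when relapse is 20% versus 30%, and becomes several times too large only when relapse in one arm approaches 50%. Means, standard deviations and ranges are distorted at lower relapse rates as well. The primary outcome and S2 are untouched. The text should be corrected before S3 is derived.

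**What to change.** Replace the duration sentence in Section 5.7.3, and merge footnote 2 into it, so that it says:

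- the duration of each fever episode is the earlier of its fever stop and 28 days after treatment initiation, minus the later of that episode's own fever start and treatment start;
- S3 is the number of days alive within the 28 days minus the sum of these durations, with any fever episode still open at death ended at death so that time after death is not subtracted twice.

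Keeping the later of the two starting times matters: fever often precedes the first antibiotic dose, and time before day 0 should not count.

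The cost is one sentence and a dated note recording the correction. Fever start is already defined in the same section, so no new data are needed, and the analysis code in Appendix A.4 does not depend on the change.
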